**Table 2: Identity of the Investigational Medicinal Products**

Drug Name	Gan & Lee Insulin Glargine Injection	Lantus®
Manufacturer	Gan & Lee Pharmaceuticals, China	Sanofi-Aventis Deutschland GmbH, Germany
Formulation	Solution	Solution
Strength	100 U/mL	100 U/mL
Route of administration	Subcutaneous	Subcutaneous

Lantus® contains insulin glargine, an insulin analog, and has a prolonged duration of action. Lantus® and Gan & Lee Insulin Glargine should be administered once daily at any time but at the same time each day. To be consistent with current Lantus® labeling, twice-daily dosing of IP is strictly prohibited. The dose regimen (dose and timing) should be individually adjusted. In patients with type 2 diabetes mellitus, Lantus® and Gan & Lee Insulin Glargine Injection can also be given together with OAMs.

Gan & Lee Insulin Glargine will be contained in Gan & Lee injector pens (3.0-mL pre-filled glass cartridge) for multiple dose administration.

Lantus® will be provided in 3.0-mL SoloStar® pre-filled pens.

Subjects will follow instructions provided by the Investigator and/or designee regarding proper dose administration of IP and use of the insulin pens, glucometer and related supplies, and the frequency of glucose testing.

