**9.10 Visit 9 (EOT Visit): Week 26 (± 3 Days)**

Subjects will visit the study site for the last time at Week 26 of the Treatment Period (Visit 9). The Investigator or designee will perform the following procedures and assessments:

- Concomitant medications and adverse events
- Review of insulin and OAM use, glucose results, and the Hypoglycemic Events Record
- The CGM sensor that was applied at Week 25 will be collected from the subject's arm
- The 8-day Mealtime & Insulin Dose Record will be collected and reviewed
- Vital signs, body weight, and BMI
- Venous blood will be collected for the following tests:
  - Routine hematology and chemistry tests, and free T4 and TSH
  - FBG test
  - HbA1c
  - AIA (blood should be collected before the subject administers insulin)
- Urine samples will be collected for urinalysis and, for female subjects of childbearing potential, a urine pregnancy test
- 12-lead ECG
- Physical examination
- All remaining IP kits will be collected for accountability
- Any other applicable end-of-treatment procedures will be carried out

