## **11. SAFETY MEASUREMENTS AND VARIABLES**

### **11.1 Adverse Events**

The definitions and reporting procedures provided in this protocol comply with the current CFR 21 Part 312. An adverse event is any untoward medical occurrence or worsening of a pre-existing condition, regardless of the relationship to the investigational medicinal product. An adverse event can therefore be any unfavorable or unintended sign, including an abnormal laboratory finding, symptom or disease temporally associated with the use of an investigational medicinal product whether or not considered related to the investigational medicinal product.

Adverse events will be recorded beginning at the screening visit. Nonserious adverse events will be recorded from the time informed consent is signed through the subject's last study visit (or termination if the subject terminates early from the study for any reason). Serious adverse events will be collected from the time informed consent is signed through and including 30 calendar days after the last dose of treatment with IP.

The Investigator or designee will record all adverse events on the eCRF, regardless of the Investigator's assessment of causality, including a description of the event, severity, time of occurrence, duration, any action (e.g., treatment and follow-up tests), the event outcome, and the Investigator's assessment of the relationship to the study treatment.

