##### **11.5.1 Abnormal Laboratory Test Results**

Changes or abnormalities in clinical laboratory results judged to be clinically significant by the Investigator will be recorded as adverse events. If an unexplained abnormal laboratory test result occurs, the Investigator or designee will promptly repeat the test and monitor the

subject until the result has returned to the normal range or an adequate explanation of the abnormality is found.

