7.1 General

1) Actual Treatment

The actual treatment received is defined as the IP treatment the subject received during the study, regardless of the treatment the subject was allocated to by randomization. If a subject receives both Gan & Lee Insulin Glargine Injection and Lantus® during the study period for whatever reason, then the actual treatment will be based on the treatment taken on the majority of days during the study.

2) Assessment after EOT

Assessment after EOT is defined as AIA/HbA1c assessment documented after date of EOT visit. If date of EOT visit is missing it is defined as assessment documented after date of last dose of IP + 1 day (to consider assessments of subjects who perform the visit assessment before daily dose of IP).

3) Average Daily Dose of IP

Average Daily Dose is defined as captured on the Average Daily Dose of Study Drug CRF page.

4) Baseline

For each endpoint of interest, unless otherwise noted, the study baseline is defined as the last non-missing assessment taken prior to or on the date of the first dose of study IP. For subjects whose treatment assignment is randomly assigned but not dosed after the randomization visit, the baseline is defined as the last non-missing assessment prior to or on the date of randomization.

5) Change from Baseline

Change from baseline is defined as (value at post-baseline visit – value at baseline).

6) Completer Week 26

A subject is defined as a Completer Week 26 if the answer to the question "Did the subject complete the study?" is "Yes" on the End of Study CRF page and who received IP for at least 22 weeks.

7) Dates of First and Last Dose

The date of first dose of IP is defined as the date of first dose of IP documented on the First Dose of Study IP CRF page and the date of last dose of IP is defined as the date of last dose of IP documented on the End of Study 2 CRF page. If no date of first dose of IP is available, the date of randomization will be selected as the date of first dose of IP. If no date of last dose of IP is available, the date of completion/discontinuation documented on the End of Study CRF page will be selected as the date of last dose. If date of last dose of IP is not available and subject is lost to follow up based on End of Study CRF page, date of last scheduled visit or date of last telephone contact where an average daily dose is recorded, will be used as the date of last dose of IP.

8) Diabetes Disease Duration

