7.3 Safety

1) American Diabetes Association (ADA) Severe Hypoglycemic AE

A hypoglycemic AE will be classified as "ADA severe" if the answer to the question "Was third party intervention required for this episode of hypoglycemia?" is Yes on the Hypoglycemia CRF page as mentioned in the ADA hypoglycemia position statement (3).

ADA Severe Hypoglycemic AE should not be confused with hypoglycemia AEs that are graded severe (Grade 3) per National Cancer Institute Common Terminology Criteria for Adverse Events (NCI CTCAE) grade (see Section 11.8.1.1).

2) Adverse Event Leading to Discontinuation of IP

An AE will be classified as an AE leading to discontinuation of IP if the answer to the question "Did the adverse event cause the subject to be discontinued from the study?" is Yes on the AE CRF page.

3) Hypoglycemic AE

An AE will be classified as a hypoglycemic AE if the answer to the question "Is this a hypoglycemic event?" is Yes on the AE CRF page.

4) Injection Site Reactions

Injection site reactions will be identified using the High Level Term = "Injection site reactions".

5) IP-related adverse events

An AE will be classified as related to IP if the relationship to study treatment is Possibly Related, Probably Related, or Definitely Related. Additionally, if the relationship is missing, then the AE will be deemed related to IP.

6) Measured Hypoglycemic AE

A hypoglycemic AE will be classified as measured if the lowest blood glucose value documented on the Hypoglycemia page is less than or equal to 3.0 mmol/L.

7) Persistent/Non-persistent Hypoglycemic AE

Hypoglycemic event with Time in hypoglycemia (see definition in Section 7.4) greater or equal to an hour (per CGM) would be classified as persistent. A hypoglycemic event with Time in hypoglycemia below an hour (per CGM) would be classified as non-persistent.

8) Symptomatic Hypoglycemic AE

A Hypoglycemic AE will be classified as symptomatic if the answer to the question "Was subject aware of symptoms?" is Yes on the Hypoglycemia CRF page.

9) Treatment-emergent adverse events (TEAE)

A TEAE is defined as an AE occurring on or after the date of the subject's first dose of IP and on or before the day of last dose for AEs but not more than 30 days after the subject's last dose of IP for SAEs.

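### The treatment-emergent window for non-serious AEs closes on the calendar day of last dose, so events starting the next day drop out of the TEAE summaries

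*SAP*

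**What the plan says.** SAP 7.3, definition 9, opens the treatment-emergent window on the date of first dose. For non-serious events the window ends "on or before the day of last dose for AEs". For serious events the limit is "but not more than 30 days after the subject's last dose of IP for SAEs". There is no lag for non-serious events.

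Protocol 11.1 sets a longer collection period: "Nonserious adverse events will be recorded from the time informed consent is signed through the subject's last study visit", or through termination if the subject leaves early.

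Other passages bear on the timing:

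- Protocol 8.5.1, under Table 2, says both products "should be administered once daily at any time but at the same time each day".
- Protocol 9.10 (Week 26) has the antibody sample taken before insulin, takes back the remaining product, and includes an ECG, a physical examination and laboratory tests.
- Protocol 11.5.1 says of laboratory results: "Changes or abnormalities in clinical laboratory results judged to be clinically significant by the Investigator will be recorded as adverse events". Sections 10.2, 10.4 and 11.5.2 say much the same for physical examination and ECG findings.
- SAP 7.1, definition 2, deals with antibody and HbA1c assessments after end of treatment. If the visit date is missing, "it is defined as assessment documented after date of last dose of IP + 1 day", and the stated reason is that some subjects are assessed before that day's dose.
- SAP 11.8.1 puts AEs outside the window in a separate listing. It compares hypoglycemia rates with a negative binomial model whose offset is the log of follow-up time, and it does not define that time.

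**The concern.** A once-daily basal insulin is still acting on the morning after an evening injection. Hypoglycemia is the adverse event of special interest (Protocol 11.3), and Protocol 8.5.8.3 says that early-morning episodes are to be expected with the reference product. A window that closes at midnight on the last-dose day can therefore label an on-drug event as not treatment-emergent.

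Two other kinds of event are exposed. A non-serious event that starts the morning after a dose and makes the subject stop has its onset after the last dose, so it drops out of the TEAE table of events leading to discontinuation. A physical-examination, ECG or laboratory AE dated to a Week 26 visit held the day after the last dose also falls outside.

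At stake are the completeness of the TEAE tables and of the hypoglycemia comparison. The SAP gives no reason for a zero-day lag.

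**Working it through.** There is no stated figure to reproduce, because the point concerns a date rule. The check applies the rule literally.

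**1. The rule.** With L the calendar date of last dose:

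- a non-serious AE is a TEAE if its onset date is no later than L;
- a serious AE is a TEAE if its onset date is no later than L + 30 days.

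The test uses the onset date. The date on which the event is found or reported does not enter.

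**2. Share of the last dosing interval that is excluded.** If the last injection is at clock hour h, then 24 − h hours of the next 24 fall on day L and are included, and h hours fall on day L + 1 and are excluded. The excluded share is h/24. The documents give no clock times, so these are assumptions.

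| Last injection | Excluded share, current rule | Excluded share, L + 1 day |
|---|---|---|
| 08:00 | 8/24 = 33% | 0% |
| 12:00 | 12/24 = 50% | 0% |
| 18:00 | 18/24 = 75% | 0% |
| 22:00 | 22/24 = 92% | 0% |

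**3. Visit scenarios.**

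| Onset of event | Current rule | L + 1 day |
|---|---|---|
| Week 26 visit day, last dose that day | TEAE | TEAE |
| Week 26 visit day, last dose the day before | not a TEAE | TEAE |
| Early termination visit 14 days after last dose, non-serious | not a TEAE | not a TEAE |
| The same event, serious | TEAE | TEAE |

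**4. Observation time lost.** For a completer whose last dose was the day before Week 26, it is 1/182 = 0.5%. For an early discontinuer seen 14 days after the last dose (Protocol 9.11 allows up to 14 days from withdrawal or discontinuation), the gap is 14 days, or 14/182 = 7.7% of the planned period. Much of that gap is time off study insulin.

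**5. Missing dates.** Under SAP 7.1, definition 7, a missing last-dose date is normally replaced by the completion or discontinuation date. A subject with a missing date can then have a longer window than one with a recorded date.

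**6. Rate model.** The current non-serious window contains L − F + 1 days, where F is the first-dose date. If follow-up time instead runs to the last visit, the denominator includes days on which non-serious events cannot be counted. The SAP does not say which period is used.

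**The case against.** The case for leaving the rule alone is that an on-treatment window is a legitimate choice. Protocol 11.1 governs what is recorded and sets no end for treatment-emergence, so a collection period longer than the analysis window is not a contradiction. That stands. What is missing is a reason for a zero-day lag with a once-daily basal insulin.

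A reader might infer that everything found at Week 26, or within a day of the last injection, is lost. The documents do not support this. Onset is what counts: an event reported at Week 26 that began by the last-dose day is included, and so is any event on that day.

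A reader might also infer that the end-of-study safety assessment disappears from the safety tables. It does not. SAP 11.8.3 to 11.8.5 summarise Week 26 laboratory, vital-sign and ECG values with no last-dose cut-off, and SAP 11 tabulates early end-of-treatment visits under Week 26. The CGM hypoglycemia summaries in SAP 11.7.3 also do not use the TEAE window. Excluded AEs are still listed, and hypoglycemic events on the Hypoglycemia CRF page are listed as well.

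Nor do the documents establish that the last dose usually precedes the Week 26 visit by a day. Sampling before insulin and the return of remaining product make it plausible, but a subject could dose at the visit after sampling.

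The allowance in SAP 7.1, definition 2, is not a safety window. It covers antibody and HbA1c assessments only, and only when the visit date is missing. It does show that the authors foresaw visits held before that day's dose.

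**Conclusion.** The point holds in limited form. Non-serious AEs with onset on the calendar day after the last dose are collected but kept out of the TEAE summaries and the hypoglycemic TEAE analyses, and appear only in listings. Some of these events occur within 24 hours of the last injection, while the once-daily dose is still acting.

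The effect is small for completers, about 1 day in 182 where the last dose was the day before the visit. It can matter more for individual events around discontinuation, and SAP 5.1 reports a larger than expected early discontinuation rate. How many events are affected cannot be known from the documents. The 33% to 92% range rests on assumed injection times.

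A reader might infer bias between arms. The documents do not show it: the same rule applies to both groups. A reader might also conclude that the window should run to the end-of-treatment or early termination visit. That does not follow, because such a visit may come up to 14 days after withdrawal, when the subject may be off study insulin or on another insulin.

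**What to change.** - In SAP 7.3, definition 9, end the non-serious window at date of last dose + 1 day, in line with the allowance in SAP 7.1, definition 2. Keep 30 days for serious events.
- In SAP 11.8.1, define the follow-up time in the negative binomial offset so that it covers the same window as the event count: from first dose to last dose + 1 day, or to the end of non-serious AE collection if that is earlier. State which window applies to serious hypoglycemic events, since the TEAE definition lets them count for up to 30 days.
- If wanted, add a supportive TEAE summary that runs to the end-of-treatment or early termination visit, labelled as including time off treatment.

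The cost is one changed phrase, one added definition and a small programming update. No new data are needed, because Protocol 11.1 already collects these events through the last visit. The downside is that a few events starting just after treatment will be counted, in both arms.

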7.4 Exploratory

1) Continuous Glucose Monitoring Device Day of Wear

The Day of wear will be defined as starting exactly $(x-1)*24$ hours and ending $x*24$ hours after the time of the first assessment at the given visit, where x is the Day of wear from 2 to 8 days.

Sponsor: Gan & Lee Pharmaceuticals, USA Corporation
Protocol no: GL-GLAT2-3002

Statistical Analysis Plan
Version Date: 16-Nov-2020

2) Time in hypoglycemia

The time in hypoglycemia will be defined using the CGM data from days 2 through 8 of wear at each of the 3 visits where CGMs are applied as the sum of the time where the glucose value is ≤ 3.0 mmol/L.

$$\sum_{i=1}^{n_T} I_{GC_i}(t_{i+1} - t_i)$$

where I_{GC_i} represents the indication of whether or not the glucose concentration at time i is ≤ 3.0 mmol/L, t_i represents the i^{th} time point (the difference between each time point will be 15 minutes), and n_T represents the number of time points for a given subject and visit and can vary based on subject and visit.

3) Time in hyperglycemia

The time in hyperglycemia will be defined using the CGM data from days 2 through 8 of wear at each of the 3 visits where CGMs are applied as the sum of the time where the glucose value is ≥ 8.9 mmol/L.

$$\sum_{i=1}^{n_T} I_{GC_i}(t_{i+1} - t_i)$$

where I_{GC_i} represents the indication of whether or not the glucose concentration at time i is greater than or equal to 8.9 mmol/L, t_i represents the i^{th} time point (the difference between each timepoint will be 15 minutes), and n_T represents the number of time points for a given subject and visit and can vary based on subject and visit.

4) Time in euglycemia

The time in euglycemia will be defined using the CGM data from days 2 through 8 of wear at each of the 3 visits where CGMs are applied as the sum of the time where the glucose value is >3.0 mmol/L and < 8.9 mmol/L.

$$\sum_{i=1}^{n_T} I_{GC_i}(t_{i+1} - t_i)$$

where I_{GC_i} represents the indication of whether or not the glucose concentration at time i is >3.0 mmol/L and <8.9 mmol/L, t_i represents the i^{th} time point (the difference between each time point will be 15 minutes), and n_T represents the number of time points for a given subject and visit and can vary based on subject and visit.

8. Analysis Sets

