6.4 Exploratory Endpoints

- Retrospective CGM hypoglycemic rate
- Time in hypoglycemia and hyperglycemia event based on CGM data

7. Definitions

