11.7.3 Exploratory Variables

11.7.3.1 Retrospective Hypoglycemic Rate

In addition to the analysis of hypoglycemic events from the AE data, a retrospective analysis of the CGM data will be performed to identify hypoglycemic events that may have gone unnoticed by the subject (Table 6, Analysis 1). A retrospective CGM-hypoglycemic event will be defined as anytime the glucose concentration decreases below the threshold of ≤ 3.0 mmol/L. This definition is supported by Seaquist et al (8). Multiple hypoglycemic events while a subject is wearing the CGM device may occur and are defined as having a glucose concentration that returns to > 3.0 mmol/L before decreasing below the threshold again. The number of hypoglycemic events detected between days 2 through 8 of CGM wear for each subject at each visit will be summarized descriptively in the SS. A listing of the CGM-hypoglycemic events including the lowest glucose concentration during the event will be provided.

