11.7.3.2 Retrospective Time in Hypoglycemia/Hyperglycemia

The time in hypoglycemia/hyperglycemia/euglycemia will be summarized with descriptive statistics at each visit and overall using the SS (Table 6, Analysis 2).

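### CGM time in hypo-, hyper- and euglycemia and the CGM hypoglycemic 'rate' are not divided by recorded sensor time, so less data lowers every one of them

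*SAP*

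**What the plan says.** SAP 6.4 lists two exploratory endpoints: "Retrospective CGM hypoglycemic rate", and time in hypoglycemia and hyperglycemia based on CGM data.

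SAP 7.4 (definitions 2 to 4) sets out the times. Time in hypoglycemia is taken "as the sum of the time where the glucose value is ≤ 3.0 mmol/L", time in hyperglycemia "as the sum of the time where the glucose value is ≥ 8.9 mmol/L", and time in euglycemia "as the sum of the time where the glucose value is >3.0 mmol/L and < 8.9 mmol/L". All three use the same formula: an indicator for the range multiplied by the step to the next reading, added up over n_T readings. On the spacing, the SAP says that "the difference between each time point will be 15 minutes". On n_T, it says that this "represents the number of time points for a given subject and visit and can vary based on subject and visit".

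SAP 11.7.3.1 is headed as a rate, but what it reports is a count: "The number of hypoglycemic events detected between days 2 through 8 of CGM wear for each subject at each visit will be summarized descriptively". SAP 11.7.3.2 says that the three times "will be summarized with descriptive statistics at each visit and overall using the SS". It does not say how visits are combined for the overall summary.

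Neither SAP 7.4, 11.7.3.1 and 11.7.3.2 nor Protocol 12.10 gives a denominator, a percent-of-wear measure or a minimum amount of data.

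**The concern.** A sum of hours in a range depends on two things: the share of time the subject spends in the range, and how long the sensor recorded. Only the first describes glycemic control. The SAP acknowledges that the second varies and then leaves it in the endpoint. The same applies to an event count reported under the name of a rate.

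The SAP treats reported hypoglycemia differently. In SAP 11.8.1 the negative binomial model for hypoglycemia events uses log follow-up time as an offset, so that unequal exposure is accounted for. The CGM measures have no equivalent.

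What is at stake is the reading of the CGM tables. A reader comparing hours or counts between arms, or between visits, cannot tell a difference in glucose from a difference in wear.

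**Working it through.** The plan gives no numerical figure for these endpoints, so there is nothing to reproduce. The check applies the SAP's own formula to subjects with identical glucose and different amounts of data.

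**Inputs from the documents**
- Window: days 2 to 8 of wear (Protocol 8.1; SAP 7.4, definition 1), that is 7 × 24 = 168 h.
- Spacing: 15 minutes (SAP 7.4), so a full window has 168 × 4 = 672 readings.

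**Assumptions** (the documents give no CGM results or wear data)
- 2% of readings at or below 3.0 mmol/L, 40% at or above 8.9 mmol/L, 58% between, and 4 events per week.
- Recorded time between 2 and 7 days.

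**Formulas**
- Raw time in range = share in range × n_T × 0.25 h = share × recorded hours.
- Raw count = events per week × recorded days / 7.

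| Days recorded | Hours | Hypoglycemia | Hyperglycemia | Euglycemia | Events |
|---|---|---|---|---|---|
| 7 | 168 | 3.36 h | 67.2 h | 97.4 h | 4.0 |
| 5 | 120 | 2.40 h | 48.0 h | 69.6 h | 2.86 |
| 3.5 | 84 | 1.68 h | 33.6 h | 48.7 h | 2.0 |
| 3 | 72 | 1.44 h | 28.8 h | 41.8 h | 1.71 |
| 2 | 48 | 0.96 h | 19.2 h | 27.8 h | 1.14 |

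Every row is the same glucose profile. Within one visit, 7 days against 3 days is a factor of 7/3 = 2.3 on all four measures. Halving the wear halves all four: hypoglycemia, hyperglycemia and events look better, while euglycemia falls from 97.4 h to 48.7 h and looks worse.

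**Other profiles.** The proportion depends only on recorded time, not on the assumed shares. At 1% of readings low, hypoglycemia time is 1.68 h over 7 days and 0.01 × 72 = 0.72 h over 3 days. At 5% it is 8.4 h and 0.05 × 72 = 3.6 h.

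**Arm level.** With identical glucose and a mean wear of 7 days in one arm, the ratio of raw means is 6.5/7 = 0.93, 6/7 = 0.86 or 5/7 = 0.71 if the other arm averages 6.5, 6 or 5 days.

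**After dividing by recorded time.** Every row of the table returns 2%, 40%, 58% and 4.0 events per week.

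**The case against.** The best defence has four parts.

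1. **The design limits variation in wear.** There is a common window of days 2 to 8, the sensor is blinded to the subject and needs no action, it can be worn for up to 14 days, and site staff remove it at Weeks 12 and 26. This stands as a limit on size. It caps the recorded time at 168 h but does not equalize it, and the SAP itself expects n_T to vary.

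2. **The denominator is partly recoverable.** The three ranges are exhaustive, so their sum is the recorded time. From the planned by-visit means a reader could add the three and obtain mean wear by arm. This stands for means. It does not work for medians, percentiles or subject-level shares, and it leaves the reader to do the analysis.

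3. **The consequences are small.** The endpoints are exploratory and descriptive, with no test or margin, and CGM does not guide treatment. This stands in full.

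4. **The table shells are a separate document** (SAP Appendix 3) and might show percentages or per-day values. That cannot be checked here. The definition still belongs in the SAP, and the one given there has no denominator.

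A reader might also go further than the text allows:

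- **Less data makes a subject look better controlled throughout.** This is not so for euglycemia, which moves the other way.
- **Early dropouts pull down the by-visit values.** A subject with no sensor data at a visit has nothing to sum, and nothing says that such a subject counts as zero.
- **The same control can vary sevenfold.** That figure sets 0.02 × 504 = 10.1 h, three full periods added together, against 1.4 h from one short visit. SAP 11.7.3.2 does not say that the overall summary adds periods.
- **A gap in the readings is credited whole to the last value seen.** The formula could be read so, but this conflicts with the stated 15-minute spacing.

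**Conclusion.** The point holds, at minor severity. As defined, all three CGM times and the event count scale with recorded sensor time, and the endpoint called a rate is a count. The size within one visit is the ratio of recorded times: 2.3-fold for 7 days against 3, whatever the glucose profile. Between arms it is the ratio of mean wear, for example 0.86 at 6 days against 7. The wear durations and glucose shares are assumptions made for illustration.

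The documents do not support saying that the comparison between arms is biased. The arms are distorted only if wear differs by arm, and no wear data are given. Nor do they show how the overall summary would behave, because they do not say how it is formed. That silence should be filled, particularly as one of the three sensor periods precedes randomization.

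**What to change.** In SAP 7.4, 11.7.3.1 and 11.7.3.2:

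- Count 15 minutes for each valid reading in days 2 to 8.
- Report each range as a percent of valid recorded CGM time, and hypoglycemic events per day of valid data.
- Present recorded wear time by arm and visit.
- Form the overall summary from the same wear-normalized measures over the two post-randomization periods (Weeks 12 and 26), and show the screening period separately as baseline.
- A minimum-data threshold is optional. If one is wanted, the sponsor should set it before unblinding.

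The hours can be kept as an intermediate quantity, since SAP 7.3 (definition 7) refers to the 7.4 time in hypoglycemia for its one-hour cut-off.

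The cost is minor reprogramming on data already collected. The downside is that percentages and daily rates are less precise for subjects with short wear. The wear table makes that visible.
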